# **Strategies for Recruitment and Retention**

A total of 120 participants (age 55-85 years) will be recruited for completion of the proposed study. Subjects that meet inclusion criteria will be randomized into one of two diet groups, the MMKD or AHAD. The AHAD group will serve as the control group and the MMKD the intervention group, each with a target of 60 participants.

A standardized phone screen questionnaire will be used to determine basic eligibility. Potential participants who pass this initial screen will then receive an in-person screening, consisting of physical/neurological exam, medical history, and neuropsychological exams to confirm an aMCI diagnosis. All clinical data will be reviewed by expert study physicians and neuropsychologists. Clinical laboratories and physical/neurological exam will be performed, or may be reviewed from a clinic visit within the last 6 months, in order to exclude patients with major medical disorders.

Additionally, participants that gave blood in the past 56 days must agree to abstain from donating blood for the duration of the study. Study visits will not be scheduled until 56 days after the most recent donation.

## Subject Recruitment Methods

Our lab has had ample success in recruitment for its clinical studies, thus current recruitment methods for other lab studies will be used. These methods include newspaper advertisements in the Winston Salem Journal and The Chronicle, radio advertisements, postcards, website, the Memory Assessment Clinic (MAC) at Wake Forest Baptist Medical Center and community talks in churches and retirement communities. Males and females will be comparably represented, and every effort will be made to enroll an ethnically diverse sample that typifies the geographical region. Recruitment through talks and print/radio ads will be targeted at the minority populations and women in order to ensure representative enrollment in these populations.

Once participants have been identified as potential study candidates, they will be contacted by telephone by the study coordinator. The study coordinator will explain the nature of the study and the study procedures by reviewing the material presented on the consent form. Potential participants who express interest in the study will be asked to meet with the coordinator and a study nurse, at which time the consent form will be reviewed again and questions or concerns about the study will be addressed.

Potential participants for this trial may also be recruited through other studies ongoing in our lab, including the Alzheimer's Disease Core Center (ADCC). Participants who have participated in other clinical trials, such as the ADCC study, within the past 3 months will not have to repeat clinical labs, screening cognitive tests, MRI, LP, and DEXA during their screening/baseline visits. The data previously collected for the ADCC study will be used.

## **DIET INTERVENTION**

#### Interventions and Interactions

All potential participants for the study will first undergo a screening visit. Upon enrollment participants will have a total of three Core study assessments (data may be collected over several days for each Core assessment as long as visits are completed within two weeks – imaging, LP, etc.) occurring at baseline, 8 and 17 weeks (on-diet assessments), and 24 weeks (post-diet follow-up assessment). In addition to Core study visits participants will have weekly diet education visits for the first eight weeks, then return at 12 weeks to assess diet compliance over the course of the diet intervention. On week's 9-11 and 13-16 participants will have weekly telephone contact with the study dietitian to discuss food selection, meal preparation and any issues with diet compliance.

## **Experimental Diet**

We will use a Modified Mediterranean-Ketogenic Diet (MMKD), which is a very low carbohydrate diet (<20 grams/day) aimed at inducing ketosis, as the experimental diet in the proposed study. We will use a modified American Heart Association Diet (AHAD), which is a low fat diet (<40 grams/day) as the control diet. The amount of carbohydrate (and fat) will be the main variable manipulated between the two diets. The target macronutrient composition (expressed as % of total calories) is approximately 5-10% carbohydrate, 60-65% fat, and 30% protein for the MMKD; and 55-65% carbohydrate, 15-20% fat, and 20-30% protein for the AHAD. Participants on the MMKD will be asked to keep their daily carbohydrate consumption below 20 grams per day throughout the 4-month intervention and the amount of fat and protein may be variable. Higher fat foods (preferably low in saturated fats) will be added liberally to the diet plan. Throughout the duration of the study, participants on the MMKD will be encouraged to avoid low-carbohydrate store brought products and artificially sweetened beverages. The MMKD group will be supplied with extra virgin olive oil during their in person visits to use as a source of fat in their diet, and will be encouraged to eat plentiful fish, lean meats, and nutrient rich foods that meet the requirement of <20 grams total carbohydrates per day. The results of the recent PREDIMED trial have showed benefits with extra virgin olive oil supplementation on cardiovascular disease risk and mortality. Participants on the AHAD will be encouraged to limit their amount of fat intake to <40 grams/day, while eating plentiful fruits, vegetables, and carbohydrates containing adequate fiber. Participants will be encouraged to consume the same amount of calories as their prestudy diet.

Participants on both diets will receive the same daily multivitamin supplement (Centrum Silver) over the course of the study and instructed to take 1 tablet each day while on both diets. Moreover, the following supplements should be discontinued for the duration of the study: resveratrol, CoQ10 (coenzyme Q10), coconut oil/other medium chain triglyceride-containing (ie: Axona) supplements, or curcumin, as they may impact bioenergetic status and interfere with interpretation of study results.

**Diet Implementation and Monitoring:** A dedicated registered dietician will develop daily meal plans for each study participant based upon their food preferences and caloric needs as determined by resting metabolic rate assessment, pre-study food records, and activity levels. The dietitian will work with an existing portfolio of more than 400 recipes that meet the macro-nutritional requirements for each diet. Participants will have weekly in-person visits for the first two months where a food diary will be reviewed and compliance rated, followed by monthly in-person visits, with phone calls on the off

weeks; food diaries will be completed at least 3x per week and include food/drink description and volume. Capillary ketone and glucose levels will also be measured in person weekly for the first two months, then monthly. If compliance is not satisfactory based on ketone measurements or food diary review, weekly in-person visits will be reinstated. Participants will be required to supply their own food based upon a daily meal plan, food list, and other educational material provided. A food stipend of \$25 per week will be given to participants to help defray food cost, and a food scale to aid in food preparation. Participants will be asked to keep their exercise stable throughout the study. We have used these methods in our pilot study and found that they were highly successful in achieving dietary targets and maintaining compliance. Less than 10% (2 of 21) of participants discontinued our pilot study and the remaining participants showed good compliance. Because participants will be encouraged to maintain their normal caloric intake, they will experience minimal weight change throughout the intervention. We have defined weight stable as ±5 pounds. Weight will be monitored at each study visit, and caloric recommendations adjusted to ensure weight stability.

# Storage and Distribution of Study Supplements

The multivitamins and olive oil provided to participants in the study diet groups will be stored within the Sticht Center at Wake Forest University School of Medicine. The supplements will be kept within a locked area on the first floor Kulynych Research Center. Participants on the MMKD will receive olive oil as needed at their in-person study visits. The olive oil will be used as an added fat source. All participants in the diet study will receive Centrum Silver multivitamin tablets at baseline to take throughout the study.

**Blinding:** Although it is not possible for participants and the dietitian to be blinded to the study diet, all study personnel involved in performing cognitive testing or other outcome procedures or data analysis will be blinded. Participants will receive equal attention and instruction regarding their diets, and must expend similar amounts of effort to comply with dietary requirements. It will also be emphasized to participants that both diets may reasonably be expected to provide health benefits.

## STUDY PROCEDURES AND SCHEDULE

**Screening and Enrollment**: Following a 12-hour fast, prospective participants will arrive at the Clinical Research Unit at the Sticht Center for Healthy Aging and Alzheimer's Prevention and sign informed consent. Participants will then undergo the following screening procedures to confirm eligibility: brief cognitive screening assessment, blood draw for screening labs (CBC, CMP, LFTs, lipid panel, calcium, thyroid stimulating hormone (TSH), B12, and PT/INR), blood pressure, height/weight, and a brief physical exam and questionnaires.

Following the screening visit, the eligibility of the participant for enrollment will be determined by the study physician and an expert consensus panel. Once a participants has been enrolled they will be asked to complete a physical activity log and 3-day food diary prior to their first diet education visit. These measures will be used to determine basic information about physical activity level, chronic caloric intake and typical pre-study dietary habits. Participants will continue to adhere to a self-selected, ad-libitum diet until the diet intervention begins.

Note: Screening data from other center studies may be used if a prospective participant is interested in the study. These data are valid as long as it was acquired within 6 months of the baseline visits for this diet study.

**Core Study Visits:** The Core study visits will be scheduled to begin within a two-week period before the diet intervention begins. The Core study visits include the Pre-Diet visits, Mid-Diet visit, the Post-Diet visits, and the Post-Diet Follow-up visit. The Core study visits will include a combination of the

following study measurements: DEXA scan, amyloid and dual tracer PET, structural/functional MRI, lumbar puncture (LP), cognitive testing, blood draw, capillary glucose/ketone testing, and stool collection.

**Pre-Diet Study Visits:** The Pre-Diet Study Visits will occur during 2 weeks prior to the start of the assigned study diet. At these visits, cognitive assessment, blood testing, capillary glucose/ketone testing, MRI, PET, DEXA, stool collection, and LP will occur. If the participant has not had the Apolipoprotein E (APOE) genetic test performed in a previous study, we will ask that they agree to the test and draw a sample for that purpose at the Pre-Diet visit. Once participants complete the Pre-Diet Lumbar Puncture (Visit 3) they will be randomized to a diet group.

**Mid-Diet Study Visit:** The Mid-Diet visit occurs at week 8 (Visit 13) and will include diet education and compliance check, cognitive testing, stool and blood sample collection. At this visit additional measures will be recorded such as capillary glucose/ketone testing, weight and metabolic outcomes.

**Post-Diet Study Visits:** The Post-Diet Study Visits will occur during week 17 (Visits 15-17). At these visits, cognitive assessment, blood testing, capillary glucose/ketone testing, MRI, PET, DEXA, stool collection, and LP will occur.

**Post-Diet Follow-up Visit:** The Post-Diet Follow-up Visit will occur during week 24 (Visit 19) after participants have discontinued the diet and returned to an adlib diet. At this visit, cognitive assessment, blood testing, and capillary glucose/ketone testing will occur.

**Diet Educational Study Visits:** Over the course of the diet study, participants whether on the MMKD or AHA diet, will participate in a series of individual, group and phone educational visits to inform participants of diet specifics, develop personalized meal plans, ensure adherence to their diet, and answer any questions. The study dietician will lead these educational sessions in the clinic or by phone.

**In-Person Diet Education Sessions**: The Pre-Diet Education session will take place within 1 week prior to the start of the diet (90 min session). After diet initiation, for both diets, participants will meet with the study dietitian weekly for the firest 8 weeks of the study for continued diet education and assessment of compliance. Participants will return to the clinic at week 12 for diet education and compliance check.

If participant enrollment and scheduling permit group sessions, participants may meet as a group or individually during later weeks. These sessions will last from 30 min (individual) to 60 min (group) each and will provide participants support and the opportunity to ask questions. Diet guidelines will be reviewed at each session. However, if necessary to improve diet adherence and understanding, individual sessions with the study dietitian may take place as needed during the remainder of the study. The need for these sessions can be determined by the study dietitian and/or by participant request.

**Phone Sessions**: Each participant will have a phone session in addition to diet education with the study dietitian 3-4 days after starting the diet and again in week 2. These session will allow the participants and caregivers to ask questions and receive support as needed. Phone sessions will also occur in weeks 9-11 and 13-16, and may be increased in frequency as needed to optimize compliance.

Note: Data will be recorded at Diet Education Visits, including capillary glucose/ketone testing, weight, adverse events, diet compliance, and nutritional intake.

Table. 2. Schedule of Study Visits and Procedures

Clinic Visit #	1	2	3	4	5	6	7	8	9	10	11	12	13	14	15	16	17	18	19
Visit Week	-12		Baseline			1	2	3	4	5	6	7	8	12		17		20	24
Visit Name	Screen	Pre Cog	Pre LP	Pre dtPET	Pre amyPET	Edu	Mid Cog	Edu	Post Cog	Post LP	Post dtPET	Interm. F/U	F/U Visit						
Informed Consent	Χ																		
Demographics	Χ																		
Medical History	Χ																		
Phys/Neuro Exam	Χ																		
Screen Cognitive Battery	Χ																		
Concomitant Meds	Χ												Х		Х				Х
Resting Metabolic Rate		Х													Х				
Vital Signs	Χ	Х	Х	Х	Х								Χ		Х	Х	Х	Χ	Χ
Diet Cognitive Battery		Х											Χ		Х				Χ
Weight	Χ	Х			Х	Χ	Х	Χ	Χ	Х	Х	Χ	Χ	Χ	Х			Х	Х
Capillary Gluc/KB	Χ				Х	Χ	Х	Х	Χ	Х	Х	Χ	Χ	Х	Х			Х	Х
Blood Draw:	Χ	Х	Х						Χ				Χ	Χ	Χ	Х			Χ
APOE Genotyping		Х																	
Clinical / Safety Labs	Χ												Χ		Х				Χ
Metabolic Outcomes			Х						Χ				Х	Х	Х				Χ
Mito, Epign & Exo		Х													Х				
Blood Banking		Х	Х										Χ		Х	Х			Χ
Stool Banking		Х											Χ		Х				Χ
CSF Banking			Х													Х			
LP			Х													Х			
DEXA Scan		Х													Х				
MRI		Х													Х				
dtPET				Х													Х		
amyPET					Х														
Diet Edu. / Compliance					Х	Χ	Х	Χ	Χ	Х	Х	Χ	Χ	Х					
Food Diary		Х				Х	Х	Х	Χ	Х	Х	Χ	Χ	Х	Х				
Compliance Call						Х	Х						Χ	Х					
Adverse Events		Х	Х	Х	Х	Х	Х	Х	Χ	Х	Х	Χ	Χ	Х	Х	Х	Х	Х	Х
Safety Phone Check			Х													Х			
Sleep Battery/Monitor.		Х											Х		Χ				Χ

# **Study Visit Measures**

*Clinical/Physical Evaluation*: During eligibility screening, participants will receive standardized clinical cognitive evaluation (ADCC UDS3), a clinical interview and physical/neurological exam, clinical labs, and depression screening with the Geriatric Depression Scale (GDS). 

**Metabolic Outcomes:** Fasting plasma or serum will be sent out for assay by LabCorp diagnostic company for glucose, insulin, and lipids (total cholesterol, LDL, VLDL, HDL, triglycerides) at screening, baseline, month 2, and month 4. Quick analysis of metabolic outcomes done in week 1 and 12 or to ensure participant safety may be delivered to the Wake Forest CLIA-certified laboratory for expedited processing. Capillary ketone levels and weight will be measured at each in-person visit in the center. Body composition will be measured using DXA at baseline and at the end of the diet intervention.

**Cognitive Testing Visits:** For all cognitive visits, participants will be asked to eat a standard meal the night before and fast for 12 hours prior to start of visit. Upon arrival, weight and vital signs will be obtained and then blood will be drawn (about 3 tablespoons). A breakfast meal will then be provided (standard meal for baseline visit and study meal (MMKD or AHAD) for other visits) and the cognitive protocol will begin. All cognitive test administration will be audio-recorded.

**Cognitive Battery:** The cognitive protocol will consist of both computerized and paper-based assessments and will include all components of the memory composite as well as additional assessments. Cognitive testing will be audiotaped using a digital recorder for quality assurance and random checks will occur for quality control and to correct drift. Recordings will be erased once review has been completed. The total cognitive battery will take approximately 60-75 minutes to administer at both screening and Core Study Visits. Methods for cognitive assessments and other evaluations are described in this section.

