Human AD Studies. Several studies have examined the effects of elevating ketones with medium chain triglyceride (MCT) supplements in AD. An early study from our laboratory showed acute memory improvement after MCT consumption in adults with early AD, an effect restricted to participants without the APOE-e4 allele. In a Phase II double-blind, placebo-controlled, 3-month trial of a MCT supplement in 152 adults with early AD, participants without the APOE-e4 allele showed significant improvement on the Alzheimer's Disease Assessment Scale-Cognition (ADAS-Cog). This trial was compromised however by a high rate of gastrointestinal side effects that necessitated a protocol revision mid-trial, and resulted in a high drop-out rate in the active treatment group.

Use of a supplement to increase ketone availability is an attractive strategy due to its relative ease of implementation. However, because supplements are consumed in the context of a normal diet their efficacy may be attenuated. For example, MCT supplements do not reduce seizures in epilepsy. Pathological aspects of the typical diet such as high simple carbohydrate intake may counteract KD effects. Additionally, many nutrient-derived substances enter the brain through competitive diffusion, and thus intake of competitive substrates may attenuate the benefit of ketone supplements. In contrast, the KD promotes endogenous elevations of ketones that are readily transported into the brain. To date, only one small trial has examined the effects of a KD in adults with aMCI. Twenty-three adults with aMCI were randomly assigned to a 6-week KD or AHAD. The KD diet group showed enhanced verbal memory, as well as improved peripheral metabolism.

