## STUDY DESIGN AND ENDPOINTS

Adults with aMCI (n=120) will be randomized on a 1:1 schedule to receive either a 4-month MMKD or AHAD intervention. The MMKD and AHAD macronutrient profiles will be identical to those tested in a pilot study (IRB# 0029992). Diet interventions will be equicaloric with participants' normal diets. Personalized nutritional guidance and menus will be provided, and compliance will be assessed by a registered dietitian. Amyloid PET will be conducted at baseline. Blood collection and cognitive assessment will be conducted at baseline and after 2 and 4 months of diet. Lumbar puncture (LP), MRI and dual tracer PET will be conducted at baseline and following the intervention for all participants (see Table 1. for a list of study measures).

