## STATISTICAL CONSIDERATIONS

## Statistical Analysis and Power

Statistical analyses will be overseen by [name], Wake Forest ADCC Data Core member, who has extensive experience in the analyses of clinical trials and in using results from Phase II studies to design efficient Phase III trials. We will examine change in our primary outcome CSF AB42, using analysis of covariance to compare mean levels at 4-months between intervention groups with adjustment for baseline level, age, and MMSE. Two-sided type 1 error for the primary outcome will be controlled at 0.05 and the primary analysis (intention to treat) will include all data on participants grouped according to intervention assignment, regardless of adherence. If residuals from this model are markedly skewed, we will perform supporting analyses after data transformation. Similar approaches will be used for other secondary outcomes of our primary aim (e.g. PET, MRI, CSF). Mixed effect models will be used for repeated measures (cognition). To examine whether any differences in these outcomes are moderated by APOE genotype, amyloid PET positivity, insulin resistance (secondary aims), or by gender, we will use tests of their interaction with intervention assignment. Additional aims involve examining how changes among outcomes differ between intervention groups and whether they track with markers of hypothesized mechanisms. We will explore the intercorrelations among changes using multivariate decomposition and assess whether these differ between intervention groups. We will also assess mediation, using models in Emsley et al. 2010^84 to identify potential underlying mechanisms.

**Power Analysis for Primary Endpoints:** Sample size estimates for the proposed study were based on the results of our small pilot study showing 6-week mean MMKD vs AHAD diet changes in CSF

Aβ42 of 89 vs 11 units (pooled SD of changes 102). With 2-sided type 1 error of 0.05, if attrition is as large as 15% (our observed pilot attrition was 10%), and allowing a 10% attenuation of effect related to possible non-adherence, enrolling 53 participants/group provides >90% power: thus, we target N=60/group. The proposed longer 4-month intervention and covariate adjustment may increase power to detect a true difference.

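### As written, the breakfast rule serves each arm its own study meal before week-24 cognitive testing, so the only off-diet randomised cognitive comparison cannot separate a test-day meal effect from a lasting diet effect

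*Combined protocol and SAP*

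**What the plan says.** The breakfast rule is in Study Visit Measures, under Cognitive Testing Visits. It opens with "For all cognitive visits", asks for a standard meal the evening before and a 12-hour fast, places the blood draw first, and then states: "A breakfast meal will then be provided (standard meal for baseline visit and study meal (MMKD or AHAD) for other visits". Cognitive testing follows the meal. No other section names a breakfast for week 24.

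Interventions and Interactions classifies the later assessments as "8 and 17 weeks (on-diet assessments), and 24 weeks (post-diet follow-up assessment". Study Procedures and Schedule says the follow-up visit "will occur during week 24 (Visit 19) after participants have discontinued the diet and returned to an adlib diet", and lists cognitive assessment among its procedures. In Table 2 the row "Diet Cognitive Battery" is marked at Visits 2, 13, 15 and 19, which are pre-diet, week 8, week 17 and week 24.

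The analytic role of week 24 is not stated. Study Design and Endpoints says only that "Blood collection and cognitive assessment will be conducted at baseline and after 2 and 4 months of diet". Statistical Analysis and Power says "Mixed effect models will be used for repeated measures (cognition" without naming time points or a week-24 contrast.

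**The concern.** At weeks 8 and 17 the study breakfast is part of the assigned diet, so it belongs to the treatment being compared. At week 24 the diet has ended. If each arm still eats its own study meal just before testing, meal and arm coincide for every participant. A between-arm difference on the PACC or another performance test could then come from that morning's breakfast, from a lasting effect of four months on diet, or from both. Covariates and modelling cannot help, because the meal does not vary within arm.

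The protocol gives some reason to think that same-day intake matters. Its background on human AD studies cites earlier work showing "acute memory improvement after MCT consumption in adults with early AD, an effect restricted to participants without the APOE-e4 allele". It also standardises the previous evening's meal, the fast and the baseline breakfast.

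What is at stake is any later statement that cognitive benefit persists, or fades, after the diet stops. Such a statement could feed into the Phase III design that this trial is meant to inform.

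**Working it through.** **1. Which cognitive comparisons are randomised and off diet?** Randomisation follows the pre-diet lumbar puncture at Visit 3.

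| Visit | Week | Diet status | Battery in Table 2 | Breakfast as written |
|---|---|---|---|---|
| 2 | pre-diet | before randomisation | yes | standard |
| 13 | 8 | on diet | yes | arm's study meal |
| 15 | 17 | on diet | yes | arm's study meal |
| 18 | 20 | after the diet | no | not applicable |
| 19 | 24 | off diet, ad lib | yes | arm's study meal |

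Week 24 is the only row that is randomised, off diet and tested.

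**2. Which outcomes are not exposed?** CSF is drawn after a fast of at least 12 hours, and Table 2 has no lumbar puncture at Visit 19. Blood at cognitive visits is drawn before breakfast. Weeks 8 and 17 are on diet. Informant-rated measures such as the ADCS-ADL are less exposed than performance tests.

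**3. Reproducing the plan's own figure.** The power section for secondary endpoints gives 80% power for 0.56 SD with 60 enrolled per group. With the 15% attrition allowance, 60 × 0.85 = 51 per arm. A two-sided 0.05 t-test with 51 per arm has 79.97% power at 0.56 SD, so the stated figure assumes 51 analysed. The same n is used below.

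**4. Illustration of size.** The documents give no same-day meal effect, so d is assumed to be 0.1, 0.2 or 0.3 SD, with no lasting diet effect and an unadjusted two-sided 0.05 t-test. The noncentrality is d × √(n/2) on 2n − 2 degrees of freedom. At n = 51, √(51/2) = 5.05, giving noncentralities 0.505, 1.010 and 1.515 against a critical value of 1.984. The second n is 60 × 0.90 = 54, from the 10% pilot attrition.

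| Assumed d | 51 per arm | 54 per arm |
|---|---|---|
| 0.1 | 7.9% | 8.1% |
| 0.2 | 17.0% | 17.8% |
| 0.3 | 32.3% | 33.9% |

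**5. If only APOE-e4 non-carriers respond,** as in the MCT study, the mean effect is d × the non-carrier share. That share is assumed to be 40–60%. At 51 per arm:

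| Assumed d in non-carriers | 40% share: mean effect, significant | 60% share: mean effect, significant |
|---|---|---|
| 0.1 | 0.04 SD, 5.5% | 0.06 SD, 6.0% |
| 0.2 | 0.08 SD, 6.9% | 0.12 SD, 9.2% |
| 0.3 | 0.12 SD, 9.2% | 0.18 SD, 14.7% |

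**6. For scale,** the 95% confidence interval half-width for a week-24 difference at 51 per arm is 1.984 × √(2/51) = 0.39 SD.

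**The case against.** The strongest reply is that the rule was never meant to cover week 24. Table 2 names Visits 2, 13 and 15 as the Pre, Mid and Post Cog visits, while Visit 19 is only a follow-up visit. The design section lists cognition at baseline, 2 and 4 months. A fully literal reading would also reach the screening visit, which has a cognitive battery but precedes randomisation, so no study meal could be assigned there. The narrower reading is therefore possible. It is not compelling: Study Procedures and Schedule counts the follow-up among the Core visits, and the blood collection section groups follow-up with the pre- and post-diet cognitive visits. Staff who follow the sentence as it stands would serve arm-specific meals at Visit 19.

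The second reply is that the mechanism is unshown. This stands. The cited effect was from an MCT supplement in early AD and only in APOE-e4 non-carriers. The same background section says supplements may work less well alongside a normal diet, and the risk section places the MMKD fuel shift in the first week on diet. A single MMKD breakfast after stopping need not act like an MCT dose.

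The third reply is that the stake is small and the effect sizes are assumed. This also stands. No week-24 contrast or persistence hypothesis is prespecified, cognition would be analysed by mixed models and not a t-test, and the largest percentages come from the largest assumed effect applied to everyone.

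**Conclusion.** The concern holds. Followed as written, the protocol makes the test-day breakfast coincide with arm at the only off-diet randomised cognitive comparison, and this cannot be undone at analysis. Whether it would bias the result depends on a same-day meal effect that is plausible but not demonstrated. Under the stated assumptions, the chance of a significant week-24 difference with no lasting effect rises from 5% to between 5.5% and 34%. The low end assumes 0.1 SD in non-carriers making up 40% of the sample (51 per arm), and the high end assumes 0.3 SD in everyone (54 per arm). The consequence is confined to a secondary, exploratory contrast. The primary outcome, the fasting bloods and the on-diet cognitive comparisons are unaffected. The point deserves correction because the remedy is cheap and must come before the data are collected. Confidence is medium, because the sentence may simply be loosely worded.

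**What to change.** Reconcile the Cognitive Testing Visits paragraph with the description of the follow-up visit. State that both arms receive the baseline standard breakfast before week-24 testing, and that the study meal applies only at the on-diet cognitive visits, weeks 8 and 17. This changes an assessment condition after the diet has ended, not the assigned intervention.

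The cost is one sentence of visit procedure and a small change in meal logistics. The drawback is that each arm's own change from week 17 to week 24 would then include a change of test-day breakfast. The randomised week-24 comparison is not affected by that, because both arms eat the same meal.

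The change removes only the test-day meal. What participants chose to eat after week 17 still contributes to the week-24 comparison, and Table 2 marks no food diary at Visits 18 and 19.
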